Study Title: Online Trial Examining Validity of the Shared Decision Making Process Survey With Video Vignettes

Document Title: Design and Analysis plan for an online trial examining validity of the shared decision making process survey with video vignettes

PI: [name] ([contact])

Statistician: [name]

ClinicalTrails.gov: NCT04317274

Date: March 06, 2023

Purpose:

To examine the validity of the Shared Decision Making (SDM) Process scores in assessing SDM for cancer screening and medication decisions through standardized videos of good-quality and poor-quality SDM consultations.

Design:

Study staff are working with a national sampling firm to recruit subjects and obtain 400 responses. Subjects were randomly assigned to one of four arms. (1) Colorectal cancer screening good shared decision making video then poor video second (2) Colorectal cancer screening poor shared decision making video then good video (3) Treatment of high cholesterol good video then poor video and (4) Treatment of high cholesterol poor shared decision making video first then good video. Participants completed measures of Shared Decision Making after each video.

Randomization and Blinding:

Participants in each study were randomly assigned by the sampling firm to view videos of both good and poor-quality SDM conversations between a physician and patient actor in a specified order. Those randomized to the good-quality first group viewed the good quality SDM video followed by the poor-quality SDM video, while those randomized to the poor-quality first group viewed the poor-quality SDM video followed by the good-quality SDM video. Participants were blinded to their order, but no other blinding occurred.

Outcomes:

- SDM Process scale. The SDM Process scale measures the amount of SDM that occurs in an interaction. For this project, the scale items were adapted to be completed by an observer rather than a participant in the interaction. Scores range from 0 to 4; larger values indicate greater SDM occurred.
- Nine-Item Shared Decision Making Questionnaire. The 9-item Shared Decision Making Questionnaire (SDM-Q- 9) is a widely used patient-reported measure of SDM that focuses on the decisional process in a medical encounter. Scores range from 0 to 100; higher scores indicate more SDM occurred. The 9 items were adapted to reflect participants rating the SDM videos instead of rating their own experiences.
- Demographic and individual difference measures. Participants reported on their age, race, ethnicity, gender, income, and education. Participants were also asked to report on their health care utilization (a single item asking how many visits they had made to their health care provider in the past year; scores were truncated at 20 visits), physical health (1 = excellent, 5 = poor), and mental health (1 = excellent, 5 = poor), as well as to respond to the medical maximizer-minimizer single-item scale, a single item that measures the extent to which patients prefer to maximize or minimize the extent to which they have medical interventions.
- Individuals who watched the colorectal cancer screening videos were asked if they had ever been screened for colorectal cancer. Individuals who watched the high cholesterol videos were asked whether they have high cholesterol and if they had ever taken a medication for high cholesterol.

Sample Size:

The sample size was determined to ensure sufficient power to detect differences between the good and the poor shared decision making videos in this repeated measure design and analyses were

planned to be separate for each arm (i.e. one analysis for the colorectal cancer screening videos and a separate parallel analysis of the statins for high cholesterol video). To detect an eta² effect size of .04 with an alpha of 0.05 with 80% power would require 190 observations per clinical condition. Study staff rounded this to 200 observations per clinical condition, for a total required sample size of 400 patients.

Statistical Methods:

First, we examined descriptive statistics of the SDM Process items for the clinical conditions and orders. We examined rates of missing data to determine acceptability and descriptive results to see whether the scores span the range of total possible scores, are normally distributed, and whether there is evidence of floor or ceiling effects.

We examined the following hypotheses:

1. The good-quality SDM video will have higher mean SDM Process scores than the poor-quality SDM video in both colorectal cancer screening and high cholesterol studies, indicating discriminant validity. Multilevel models were used to test for impact of order (good quality first v. poor quality first), video (good quality v. poor quality), and the order-by-video interaction while adjusting for nesting of repeated videos within participant for the SDM Process scores.
2. The SDM Process and SDM-Q-9 scores will be at least moderately correlated (i.e., correlations $\geq .5$), indicating convergent validity. Pearson correlations were used to test for the relationship between the SDM-Q-9 and the SDM Process scores.

Heterogeneity of Treatment Effects (HTE):

Exploratory multilevel models were used to explore the relationship between order, video, and their interaction alongside other covariates, including mental and physical health status, number of visits to their health care provider in the past year, previous experience with screening (colorectal cancer screening only), previous diagnosis of high cholesterol (high cholesterol only), medical maximizer-minimizer single-item scale, education, race/ethnicity (i.e., white non-Hispanic compared to all others), income, age, and gender. All variables (except for gender, race/ ethnicity, and previous screening experience or high cholesterol diagnosis) were treated as continuous variables. All continuous variables were centered.

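### Does Hypothesis 1, worded for both clinical conditions, need more than the planned 400 participants?

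*Combined protocol and SAP*

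**What the plan says.** The Sample Size section sets out to "ensure sufficient power to detect differences between the good and the poor shared decision making videos in this repeated measure design". It says the analyses were "planned to be separate for each arm". The parenthesis that follows shows that arm here means clinical condition, with one analysis for colorectal screening and a parallel one for statins. The calculation is: "To detect an eta² effect size of .04" at alpha 0.05 "with 80% power would require 190 observations per clinical condition". This is rounded to 200 per condition, "for a total required sample size of 400 patients".

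Under Statistical Methods, Hypothesis 1 expects the good video to score above the poor one "in both colorectal cancer screening and high cholesterol studies, indicating discriminant validity". The Purpose is validity of the scores "in assessing SDM for cancer screening and medication decisions". The Design section says "Subjects were randomly assigned to one of four arms", and each arm lies within one clinical condition.

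**The concern.** Hypothesis 1 is a single numbered statement covering two conditions. Read literally, a significant result in only one of them does not satisfy it. Doubling a one-condition sample size keeps 80% power for each condition but not for the pair, because two independent tests must then both succeed. On that reading, a score that truly discriminates in both settings at the plan's own target effect would miss Hypothesis 1 about one time in three. Most of those misses would be split results, which could be misread as a lack of validity for screening or for medication decisions. The label of a total required sample size adds to the impression that 400 was meant to secure the whole hypothesis.

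**Working it through.** **Inputs.** From Sample Size: eta-squared .04, alpha .05, power 80%, 190 rounded to 200 per condition, 400 in total. From Design: different participants in the two conditions, so the two tests are independent; two ratings per participant; 400 is a count of responses obtained, so no dropout allowance enters. Not stated: sidedness, type of eta-squared, within-person correlation.

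**1. Reproducing 190.** f² = .04/.96 = .0417, f = .204. Power comes from the noncentral F(1, n−2) with λ = n·f², two-sided alpha .05.
- n = 190: λ = 190 × .0417 = 7.92, power 79.9%
- n = 191: power 80.1%
- Normal approximation: n = 188.4
- Two independent groups, standardised difference 2f = .408: 95 per group, 190 in total
- One-sided alpha .05: n = 150, which does not match

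The stated figure therefore reproduces with a two-sided test. It does so both as a paired calculation in participants and as a two-group calculation that ignores the pairing.

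**2. Power per condition at 200.** λ = 200 × .0417 = 8.33, power 81.9%. The stated 80% is met.

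**3. Power if both tests were required (partial eta-squared .04 in each condition).**
- Both: .8193² = 67.1%
- Exactly one: 2 × .8193 × .1807 = 29.6%
- Neither: .1807² = 3.3%

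For 80% on both, each test needs √.80 = 89.4%. At 249 per condition joint power is 79.9%; at 250 it is 80.1%, so the total would be 500. With 400 fixed, 80% on both holds at eta-squared .0495.

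**4. Dependence on the effect (200 per condition, same reading).**

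| Eta-squared | Each condition | Both |
|---|---|---|
| .03 | 69.7% | 48.5% |
| .04 | 81.9% | 67.1% |
| .05 | 89.8% | 80.6% |
| .06 | 94.5% | 89.2% |
| .08 | 98.6% | 97.2% |

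**5. Dependence on the reading of eta-squared.** If .04 is a share of total rating variance, the within-person test has λ = 2n·f²/(1−ρ), where ρ is the within-person correlation. The plan gives no ρ, so a range is shown for n = 200.

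| ρ | Each condition | Both |
|---|---|---|
| 0 | 98.2% | 96.5% |
| .25 | 99.7% | 99.4% |
| .5 | 99.99% | 99.98% |

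On this reading there is no shortfall at any of these values.

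**6. Text against text.** Sample Size states both its unit (the clinical condition) and its analyses (separate and parallel). Hypothesis 1 speaks of studies in the plural, and Randomization and Blinding likewise treats the conditions as separate studies. Nowhere is there a joint decision rule, a joint power figure, or a statement that validity is rejected if one condition misses significance.

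**The case for a change.** The strongest case for a change is that the hypothesis and its sample size ought to describe the same event. The wording is conjunctive, the Purpose covers both decision types, and a split result would occur about 30% of the time at the target effect with no stated interpretation. The step from 200 observations per condition to 400 patients also favours participants as the unit, which supports the paired reading behind the 67%. Splitting the hypothesis in two would cost only words.

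Much of this stands. The arithmetic is right, and the documents would read more clearly if they said that validity is judged condition by condition and named the type of eta-squared. The patient count does not settle the type of eta-squared, however, and the separate parallel analyses already tell an analyst how to treat a split result: report each condition on its own evidence. The clarification would formalise what the plan already does. The directional wording of Hypothesis 1 is not a defence: a one-sided .05 test would give 79.4% for both, but 190 reproduces only two-sided.

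**Conclusion.** The concern does not call for a change. Four hundred participants deliver what the plan states, at least 80% power in each condition (81.9% at 200 on the paired, partial eta-squared reading, two-sided alpha .05). The 67% and the 500 are correct only for a criterion the plan does not set, namely significance in both conditions, and only on that same reading with both true effects at .04. If the pairing was ignored, joint power is 96.5% at zero within-person correlation and higher at positive correlation. Even where the shortfall exists it is confined to effects near or below .04, since joint power passes 80% at about .05. Enrolling 100 more participants would repair no stated figure. Rewording the hypothesis would alter neither the multilevel models nor the condition-specific results. The loose phrasing is a gap that analysts following the separate analyses will fill sensibly.

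### Does the Hypothesis 1 model, which includes an order-by-video interaction, leave the good-versus-poor test undefined and possibly underpowered?

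*Combined protocol and SAP*

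**What the plan says.** The Design section gives each clinical condition two arms, good video then poor and poor video then good, so viewing order is counterbalanced. It says "Subjects were randomly assigned to one of four arms" and gives no allocation ratio.

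The Sample Size section aims for "power to detect differences between the good and the poor shared decision making videos in this repeated measure design", with a separate analysis for each condition. Its calculation reads: "To detect an eta² effect size of .04 with an alpha of 0.05 with 80% power would require 190 observations per clinical condition". This is rounded to 200 per condition and 400 patients in total, so one observation is one patient.

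Hypothesis 1, under Statistical Methods, predicts a higher mean SDM Process score for the good video than for the poor one, in both conditions. The model has order as its first term, followed by "video (good quality v. poor quality), and the order-by-video interaction while adjusting for nesting of repeated videos within participant". Neither the coding of order and video nor the handling of a significant interaction is stated.

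The section on Heterogeneity of Treatment Effects covers the exploratory models. It treats every variable as continuous apart from a short list of exceptions, and adds: "All continuous variables were centered".

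**The concern.** When a two-factor model contains the interaction, the meaning of the video coefficient depends on how order is coded. With order at ±1/2, it is the good-minus-poor difference averaged equally over the two orders. With order at 0/1, it is the difference in the reference order alone, estimated from about half the participants.

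Two things would be at stake if the 0/1 coefficient were taken as the test of Hypothesis 1.

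- **Power.** The sample size was set for one difference per condition using everyone in that condition. A one-order difference would be tested with well under the planned 80% power.
- **Position.** Within one order the good video is always seen first, or always second. A general drift in ratings from the first video to the second would then be mixed with the quality effect. Averaging over orders cancels such a drift, which is the purpose of counterbalancing.

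One dataset and one model could therefore give different answers to Hypothesis 1 through a choice that the plan does not record.

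**Working it through.** **Inputs.** From the Sample Size section: eta² = .04, alpha .05, power 80%, 190 required and 200 planned per condition. Assumed, because not stated: a two-sided test, 1:1 allocation to orders (100 each at 200), eta² read as partial eta² for the within-person difference, and the same true difference in both orders.

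**Step 1: the plan's own figure.** f² = .04/.96 = .0417, so the difference in units of its own standard deviation is √.0417 = .204. With noncentrality N × f² and a 1-df F test, power is .799 at N = 190 and .801 at N = 191. The normal approximation gives 189. The stated 190 is reproduced, and it belongs to the difference that uses all participants in a condition. A one-sided test would need only about 149, so two-sided is the matching reading.

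**Step 2: averaged contrast against one-order contrast.** Error df are pooled over both orders (N − 2).

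| Participants per condition | Averaged over orders | One order only |
|---|---|---|
| 190 | .204 × √190 = 2.81; power .80 | .204 × √95 = 1.99; power .51 |
| 200 | .204 × √200 = 2.89; power .82 | .204 × √100 = 2.04; power .53 |

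Power of .80 within one order would take 190 per order, or 380 per condition. In simulated mixed-model fits the mean standard error of the video term was .0997 with 0/1 coding and .0705 with centred coding, a ratio of 1.41 = √2, as expected when half the participants inform the estimate.

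**Step 3: other readings of the effect size.** If eta² is a share of total rating variance, the standardised difference is d = 2 × .204 = .408, and in within-person units d/√(2(1 − ρ)). At 200 per condition:

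| Assumed correlation ρ | One order | Averaged |
|---|---|---|
| −.3 | .71 | .95 |
| 0 | .82 | .98 |
| .5 | .98 | >.99 |

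The shortfall also fades if the videos differ by more than the design effect: at a within-person effect of .3 or .4 SD, one-order power is .85 or .98.

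**Step 4: position shift.** Let p be the second-minus-first shift in SD of the difference, and τ the true good-minus-poor effect. The good-first difference is τ − p, the poor-first difference τ + p, and the average τ. For an assumed p = .10 and τ = .204, one-order power is .18 (good first) or .86 (poor first); the average keeps .82. With τ = 0, a one-order test rejects .169 of the time, against .05 for the average. In the good-first order, .167 of that .169 favours the poor video and only .0016 would count towards Hypothesis 1. Inflated support for the hypothesis thus arises only with poor-first as reference.

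**Step 5: which contrast the text describes.** Hypothesis 1 compares two means and does not mention order. The sample-size objective does the same, and Step 1 shows that its number fits the contrast using everyone. The model sentence lists order, video and their interaction as separate effects, which is the usual language of main effects plus an interaction. No sentence proposes testing the video effect within an order.

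**The case for a change.** The strongest case for a change is that the model sentence never says averaged, that 0/1 coding in an interaction model gives something else, and that the interaction is tested with no rule for what follows. The remedy would cost two sentences, or one linear contrast from a fit already made. A larger true effect would restore power, but it would not remove position bias from a one-order estimate. The centring sentence sits with the exploratory models and cannot bind the Hypothesis 1 model.

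The omission is real, the arithmetic is right, and stating the contrast would be harmless. But the harm needs an analyst to read a reference-level coefficient as a main effect, against the wording of both the hypothesis and the sample-size objective. The only hint about coding points the other way: taken literally, the exploratory section leaves order and video off its list of exceptions, so they would be among the centred variables there. The position shifts in Step 4 have no source in the documents. Naming the averaged contrast is not a complete safeguard either. If the first video changes ratings of the second differently in the two orders, the average is biased too: with an assumed net bias of .05 or .10 SD of the difference and no video effect, it rejects .11 or .29 of the time.

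**Conclusion.** No change to the plan is needed. The test that it describes on its natural reading is the good-minus-poor difference over both orders, and for that test the sample size holds: power of about .80 at 190 and .82 at 200 per condition, under partial eta² .04, a two-sided .05 test and equal orders. The .53 figure and the position bias belong to a one-order test that the plan does not propose. The unstated coding is missing detail that analysts can be expected to fill sensibly, with ±1/2 coding or the equivalent contrast from a 0/1 fit. Anyone reading the results can check this by seeing whether the reported video effect is averaged over orders. The conclusion would differ only if the text had tied Hypothesis 1 to a single order or to the outcome of the interaction test, and it does neither.

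### Must Hypothesis 2 say whether its .5 correlation mark applies to each video or to both videos together?

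*Combined protocol and SAP*

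**What the plan says.** The Purpose section of the combined protocol and SAP sets out to examine validity "through standardized videos of good-quality and poor-quality SDM consultations". Under Design, "Participants completed measures of Shared Decision Making after each video", so each participant supplies two pairs of scores, one pair per video.

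Hypothesis 2 (Statistical Methods) reads "The SDM Process and SDM-Q-9 scores will be at least moderately correlated", with .5 as the threshold, and continues "Pearson correlations were used to test for the relationship between the SDM-Q-9 and the SDM Process scores". It does not name video, order or repeated ratings. Hypothesis 1 does: its multilevel models carry video, order and their interaction and allow for nesting within participant. The exploratory section carries the same terms: "Exploratory multilevel models were used to explore the relationship between order, video, and their interaction alongside other covariates".

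Sample Size separates the two clinical conditions. It sizes the video contrast only: an eta² "effect size of .04 with an alpha of 0.05 with 80% power would require 190 observations per clinical condition", and then "Study staff rounded this to 200 observations per clinical condition, for a total required sample size of 400 patients". No sample size is given for the correlation.

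**The concern.** A numeric pass mark needs a defined quantity, and here at least two are open. A correlation within one video asks whether viewers of the same consultation rank it alike on both scales. A correlation over both videos also asks whether both scales follow the staged difference in quality. Because the videos were made to differ, pooling could lift r above .5 even where agreement within a video is modest, and such a pass would partly repeat Hypothesis 1. If only one scale responded to the videos, pooling could instead pull r below .5. The plural in the text does not decide the matter, since it could refer to videos or to the two clinical conditions. At stake is the study's one stated criterion for convergent validity; Hypothesis 1 and the sample size are not affected.

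**Working it through.** **The plan's own figure.** From eta² = .04, f² = .04/.96 = 0.0417, f = 0.204 and d = 2f = 0.408. The normal approximation for two means gives 95 per group, 190 in all; the noncentral F test with 1 df gives 191. The stated 190 is reproduced. It sizes Hypothesis 1 and does not bear on the correlation, except as the only effect size in the document.

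**Inputs for the correlation.** The threshold (.5), two ratings per participant and 200 participants per condition come from the document. The within-video correlation r_w and the good-minus-poor shifts d1 (SDM Process) and d2 (SDM-Q-9), in within-video SDs, are not given and are assumed over a range. Within-video SDs are taken as equal for the two videos.

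**Formula.** With equal numbers of good and poor ratings,

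pooled r = (r_w + d1·d2/4) / √[(1 + d1²/4)(1 + d2²/4)].

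For equal shifts this is (r_w + x)/(1 + x), with x = d²/4. That is never below r_w, so equal shifts allow only one kind of disagreement: pooled passes and per-video fails.

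| r_w | d = 0.41 | d = 1.0 | d = 1.5 | d = 2.0 |
|---|---|---|---|---|
| .10 | .14 | .28 | .42 | .55 |
| .30 | .33 | .44 | .55 | .65 |
| .40 | .42 | .52 | .62 | .70 |
| .50 | .52 | .60 | .68 | .75 |
| .60 | .62 | .68 | .74 | .80 |

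**At the planning effect.** x = 0.408²/4 = 0.0417, so r_w = .30 gives (.30 + .0417)/1.0417 = .33. If eta² is instead a partial within-participant value, d = 0.204 × √[2(1 − ρ)], which is 0.29 at across-video correlation ρ = 0 and 0.16 at ρ = .7. Pooled r is then .31 and .30. At d = 0.41 the population verdict changes only for r_w between .5 − .5 × .0417 = .479 and .5.

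**Shift needed to change the verdict.** Setting (r_w + x)/(1 + x) = .5 gives x = 1 − 2r_w, so d = 2√(1 − 2r_w). This is 0.89 SD at r_w = .40, 1.26 SD at .30 and 1.79 SD at .10.

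**Unequal shifts.** With r_w = .30 and shifts (1.5, 0.5), pooled r is .38, so both readings fail. With r_w = .60 and shifts (1.5, 0), pooled r = .60/√1.5625 = .48, the reverse disagreement. That last case supposes that SDM-Q-9 does not move at all between videos staged to differ in SDM.

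**Simulation** (200 participants, two ratings each, across-video correlation .3 assumed). With r_w = .30, both per-video estimates fell below .5 while pooled r reached it in 93.5% of runs at d = 1.5 and in 0% at d = 0.41.

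**Is a stricter rule better?** Suppose convergent validity were claimed only if both per-video estimates reach .5. At a true r of .50 that rule passes 27% of the time. With no video shift at all it still disagrees with the pooled rule in about 25% of runs at r_w = .50 (pooled passes 51%, both-videos 26%). Near the threshold, part of any disagreement therefore comes from the decision rule and not from pooling.

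**Two ratings per person.** A Fisher 95% interval that treats the 400 ratings in a condition as independent covered pooled r in 89% to 97% of runs, for across-video correlations from 0 to .7 and equal shifts from 0 to 1.5 SD. This is a modest effect on the interval, not on the estimate compared with .5.

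**The case for a change.** The best case for a change runs as follows. Hypothesis 2 is the only stated test of convergent validity and has a fixed threshold, so its statistic ought to be fixed too. The eta² of .04 is an effect the sample can detect, not a forecast. The videos were built to contrast, so shifts of 1 SD or more are plausible, and at that size the readings can disagree. Writing down the unit costs one sentence.

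Much of this stands. The text is silent, the arithmetic is right, and .04 cannot be used to rule out large shifts. It does not show that the plan is wrong. With measures completed after each video, the per-video correlation is a natural reading, and the video contrast does not enter it. Pooling is not excluded, but no passage says that it was done.

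Nor is per-video r plainly the better choice. The Outcomes section presents the SDM Process scale as a gauge of how much shared decision making took place in an encounter, so the difference between a good and a poor encounter is arguably the variation the scale should capture. Within one fixed video only differences between viewers remain, and those may be restricted near the floor or ceiling.

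Timing also weakens the case. Recruitment is described in the present tense ("Study staff are working with a national sampling firm to recruit subjects and obtain 400 responses") and the analyses in the past, so a rule written now might well be post hoc.

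**Conclusion.** The concern does not call for a change. Hypothesis 2 leaves out the unit of its correlation and how .5 applies to several coefficients, but this is missing detail that an analyst can fill sensibly, not a faulty method. The readings differ by at most about .03 at the planning effect for a within-video r of .30. They part company only under strong shifts: with equal shifts, about 0.9 SD or more at a within-video r of .40 and 1.26 SD or more at .30. With a within-video r of .5 or above and equal shifts, both readings pass. All of this rests on assumed shifts, assumed within-video correlations and equal within-video SDs, none of which the document gives, so the effect in this study is unknown. Choosing between per-video and pooled correlation is a fair trade-off between two questions, and fixing a strict both-videos rule would bring no clear gain. The importance is minor and confined to how the Hypothesis 2 result is read.

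### The heterogeneity section has no covariate-by-video terms, so it cannot show whether the good-poor gap differs by any listed participant characteristic

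*Combined protocol and SAP*

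**What the plan says.** The effect under study is the within-participant contrast in Hypothesis 1 (Statistical Methods): "The good-quality SDM video will have higher mean SDM Process scores than the poor-quality SDM video". The Hypothesis 1 model contains order, video, "and the order-by-video interaction while adjusting for nesting of repeated videos within participant for the SDM Process scores".

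The HTE section then says: "Exploratory multilevel models were used to explore the relationship between order, video, and their interaction alongside other covariates". The possessive refers to order and video, so the interaction is the one already in Hypothesis 1. The covariates are mental health, physical health, provider visits, prior screening (colorectal) or high cholesterol diagnosis (cholesterol), and then "medical maximizer-minimizer single-item scale, education, race/ethnicity (i.e., white non-Hispanic compared to all others), income, age, and gender". That makes ten per clinical condition. The rest of the section covers coding: which variables are continuous, and "All continuous variables were centered".

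Neither this section nor any other gives a covariate-by-video product, a subgroup estimate, or an analysis stratified by a participant characteristic.

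On size, the Sample Size section says: "The sample size was determined to ensure sufficient power to detect differences between the good and the poor shared decision making videos". Its calculation reads "To detect an eta² effect size of .04" "with an alpha of 0.05 with 80% power would require 190 observations per clinical condition", rounded up to 200 per condition, with each condition analysed separately.

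**The concern.** Heterogeneity here means that the good-poor gap varies with who is watching. The stated model has no parameter for that. The only variation in the gap that it allows is by viewing order, which is a randomized design factor and not a participant characteristic.

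Two errors could follow. A significant covariate main effect reported under this heading could be read as heterogeneity when the gap is the same for everyone. A real difference in how well the scale separates good from poor consultations, for example by education or prior experience, would go unestimated. For a study whose purpose is to validate a score, the second is a natural validity question, and the heading implies that it is answered. If the aim was only covariate adjustment, the heading is what is wrong.

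**Working it through.** **Inputs from the documents.** Eta-squared .04, alpha 0.05, power 80%, 190 rounded to 200 per condition, ten covariates per condition. The documents give no SD or within-person correlation, so every SD below is an assumption. Tests are taken as two-sided.

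**1. The plan's own figure.** f² = .04/.96 = 0.0417. With a noncentral F on 1 numerator df and λ = n·f², n = 190 gives 79.9% power. The normal approximation with d = 2f = 0.408 gives 95 per group, or 190 in total. The 190 therefore reproduces. It concerns the video effect and is not in dispute.

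**2. What the stated model can estimate.** Code video v as +½ (good) or −½ (poor), order as o, and a centered covariate as x:

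Y = a + b·v + g·o + d·o·v + c·x + h·x·v + participant effect + residual

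For a participant with both scores:
- the mean of the two scores has fixed part a + g·o + c·x;
- the good-minus-poor difference has fixed part b + d·o + h·x.

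Heterogeneity by x is h. The plan's model omits h·x·v, which sets h = 0. With complete pairs, c is estimated from participant means alone and carries no information about h.

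A numerical check used 200 simulated participants with two scores each, participant and residual SD both 0.6. The main-effects model returned a video coefficient of 0.895 and a covariate coefficient of 0.138 whether the true h was 0 or 0.5. Only the model with the product term separated the two cases (estimates 0.013 and 0.513, SE 0.064).

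**3. What a main effect would suggest.** Assumptions: n = 200 complete pairs, participant SD 0.5 or 0.7, residual SD 0.6 or 0.8, effects per SD of the covariate, 4000 runs per setting.

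| Truth | c | h | Main effect significant | Covariate-by-video significant |
|---|---|---|---|---|
| (a) both videos +0.15 | 0.15 | 0 | 63-89% | about 5% |
| (b) good video only +0.3 | 0.15 | 0.3 | 64-89% | 96-99.9% |
| (c) good +0.15, poor −0.15 | 0 | 0.3 | about 5% | 96-99.9% |

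Hand check of (a) at SDs 0.5 and 0.6: the SE of c is √(0.25 + 0.36/2)/√200 = 0.656/14.14 = 0.046, so c/SE = 0.15/0.046 ≈ 3.2. That agrees with the 89% at the top of the range. The main effect cannot tell (a) from (b), and it misses (c).

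**4. What added terms could deliver.** The SE of h per SD of x is √2·σ/√200 = σ/10, where σ is the residual SD. The 95% CI half-width (about 1.97 SE) is 0.08, 0.12, 0.16 and 0.20 points on the 0-4 scale for σ = 0.4, 0.6, 0.8 and 1.0.

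Power for a gap difference per SD of the covariate:
- σ = 0.6: 91% for 0.2, 70% for 0.15, 38% for 0.1, 13% for 0.05.
- σ = 0.8: 70% for 0.2, 24% for 0.1.

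With no SD assumed, partial eta-squared can be used instead (noncentral F, df 1 and 197, λ = 200·η²/(1−η²)): 82% at .04, 52% at .02, 29% at .01. At a Bonferroni level of .05/10 = .005, power at .04 falls to 52%.

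False positives under independence: 1 − .95¹⁰ = 40% per condition, and 1 − .95²⁰ = 64% across both.

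**The case against.** The strongest reply is that the section is a short summary with no model equation. It speaks of models in the plural and does not exclude product terms. Centering is often done when products are fitted, and the heading itself suggests that they may have been. This limits what can be said about the models actually run. It does not change what the plan states: one interaction is named, it is order-by-video, and centering has other uses.

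A second reply is that the section is exploratory, with no heterogeneity hypothesis and no named moderator. That stands and limits the harm. It does not excuse an analysis from estimating what its heading names.

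Third, the two clinical conditions are analysed separately, so the gap is estimated in each. That is true, but clinical condition is not among the listed participant characteristics.

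Fourth, the simulations rest on assumed values, case (c) was built to cancel in the mean, and eta-squared .04 was set for the video effect and not for a moderator. All of this is correct. The figures are illustrations, and the conclusion rests on the algebra.

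Finally, the plan is written in the past tense, so terms added now may be post hoc, and ten of them bring multiplicity and modest power. That also stands, and it governs how the results should be labelled.

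**Conclusion.** The concern holds. Followed as written, the HTE section yields no estimate of how the good-poor gap varies with any of the ten listed characteristics. This follows from the stated model terms and needs no assumed SD. The statement that a covariate main effect reflects only the average level of the two scores assumes complete pairs. The rejection rates depend on the assumed SDs and effect sizes.

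The consequence is confined to conclusions about heterogeneity. Hypotheses 1 and 2 and the sample size are unaffected. It should be corrected, but it does not threaten the main results.

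**What to change.** Choose one of two changes.

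1. **If heterogeneity is the aim**, add covariate-by-video terms one covariate at a time, keeping order, video and order-by-video in each model.
   - Name a few key moderators first, for example prior screening or high cholesterol diagnosis, maximizer-minimizer preference and education. Treat the rest as secondary.
   - Report interaction estimates with 95% CIs as exploratory, and as post hoc if scores had already been seen.
   - State that about 200 participants per condition were sized for the video effect, and give the 40% and 64% false-positive figures.
   - Describe covariate main effects as predictors of score level, and do not read a null interaction as proof of equal discrimination.
2. **If adjustment is the aim**, retitle the section as a covariate-adjusted analysis and draw no heterogeneity conclusion from it.

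The cost is low: a few extra model terms on data already collected, or a change of heading. The price of the first option is multiplicity and limited precision.
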